2.2 Analysis sets

The Randomized Analysis Set (RAS) consists of all randomized patients. Patients will be analyzed according to the treatment they were assigned to at randomization.

The Full Analysis Set (FAS) will include all randomized patients who received at least one dose of randomized treatment. Following the intent-to-treat principle, patients will be analyzed

according to the treatment they were assigned to at randomization. It is reasonable to require that patients took randomized treatment for inclusion in the FAS because the decision on whether or not randomized treatment is started will not be influenced by the treatment group assignment due to effective treatment blinding procedures.

The Safety Set will include all patients who received at least one dose of double-blind treatment. Patients will be analyzed according to the treatment they received. If a patient received more than one double-blind treatment, e.g. QBW251 300mg and QBW251 25mg, the patient will be analyzed according to the treatment taken for the majority of days.

Note that the FAS and Safety Set are the same except that the Safety Set allows the inclusion of non-randomized patients who receive double-blind treatment in error. In addition, analyses based on the FAS assigns randomized treatment while analyses based on the Safety Set assigns received treatment.

The PK set will include all patients with at least one evaluable drug concentration data sample. The PK serial sub-group will include all patients with at least one evaluable drug concentration data sample and who consented to participate in the PK serial sub-group. Patients will be analyzed according to the treatment received for both sets.

2.2.1 Subgroup of interest

Subgroup analyses of primary endpoint and selected secondary endpoints (E-RS cough & sputum scores) will be performed.

For tables presenting results from statistical models, the treatment effects in the subgroup will be derived using the appropriate interaction terms in the model and additional covariate as a fixed effect if necessary. For subgroup analyses by severity of airflow limitation, run-in post-bronchodilator FEV₁ will be removed from the model.

The following subgroups will be used for supporting analyses:

- Smoking status (current, former)
- Severity of airflow limitation (moderate, severe)

2.3 Patient disposition, demographics and other baseline characteristics

2.3.1 Patient disposition

The RAS will be used for the summary and listing of patient disposition. The screening disposition and the analysis sets table will be based on all screened patients.

The number of patients in the RAS will be summarized by region, country, center and treatment group. Further, the overall number of patients who entered completed, and discontinued study will be summarized including the reasons for discontinuation for each period: pre-randomization, double-blind treatment and follow-up.

Number of patients with protocol deviations will be tabulated by category (e.g., selection criteria not met, subject not withdrawn as per protocol, treatment deviation, prohibited concomitant medication, other) and deviation.

The number of patients included in each analysis set will be tabulated. Patients exclusion from analysis sets will be listed for all patients with reasons for exclusion (i.e. including both protocol and non-protocol deviations).

2.3.2 Patient demographics and other baseline characteristics

Demographics and baseline characteristics will be summarized and listed using the RAS.

Demographic and baseline characteristics including age, gender, race, ethnicity, region (Latin and South America, Eastern Europe, Western Europe, Asia and Australia, North America), height, weight, body mass index (BMI), duration of COPD (as time span between date of diagnosis of COPD to date of enrollment), run-in spirometry (FEV₁, FVC, FEV₁/FVC and % of predicted FEV₁ pre- and post-bronchodilator, FEV₁ reversibility), severity of COPD (GOLD 2018), COPD exacerbation history, COPD assessment test (CAT) score, smoking status and history, vaping history, assigned background medication (Relvar+Incruse, Trelegy), , and cardiovascular risk factors at baseline will be summarized.

Summaries of continuous variables like age will include mean, standard deviation (SD), first and third quartile, median, minimum and maximum. Summaries of categorical variables will show absolute (n) and relative (%) frequencies including a category for missing data if any.

No statistical analyses will be provided for baseline comparability among the treatment groups.

In addition, the following categorizations of continuous variables will be done:

- Age into 40 - 64 years, and ≥ 65 years;
- BMI into ≤ 30.0 kg/m² and > 30.0 kg/m²;
- Duration of COPD into < 1 year, 1 - 5 years, $> 5 - 10$ years, $> 10 - 15$ years, $> 15 - 20$ years, and > 20 years;

- Severity of airflow limitation: pre-bronchodilator FEV₁ % predicted values into $< 30\%$, 30 - $< 50\%$, 50% - $< 80\%$, and $\geq 80\%$ ($< 30\%$ and $\geq 80\%$ will only be included in case of protocol deviation).
- CAT into (1 - 9 mild, 10 - 20 moderate, 21 - 30 severe, 31 - 40 very severe) (mild will only be included in case of protocol deviation)

2.3.3 Medical history/current medical condition

Medical history will be coded with the Medical Dictionary for Regulatory Activities terminology (MedDRA) using the most recent version at the time of database lock. History/conditions, including pre-specified protocol solicited events (pulmonary diseases and cardiovascular events), will be summarized for the RAS by primary system organ class and preferred term. In addition pulmonary diseases and cardiovascular events will be summarized be pre-specified medical history term.

2.4 Treatments (study treatment, rescue medication, concomitant therapies, compliance)

All summaries of treatments will be performed on the Safety Set.

2.4.1 Study treatment / compliance

The duration of exposure in days to each treatment group (QBW251 dose or placebo) will be summarized by means of descriptive statistics.

Duration of exposure to double-blind treatment will be calculated as the number of days between the first dose date and the last dose date exposed to that treatment over the specified period (expressed as: Duration of exposure = Date of last known dose of double-blind treatment – Date of first dose of double-blind treatment + 1).

The number of patients who permanently discontinued from double-blind treatment and the reasons will be summarized by treatment group. Patients who permanently discontinued from double-blind treatment will be listed including reason and date of discontinuation.

Compliance will be calculated as the percentage of the number of days where double-blind treatment was administered as per protocol (i.e., one dose in the morning and one dose in the evening) divided by the duration of exposure (i.e., the number of days between first and last dose).

Compliance will be categorized by < 80 % and 80 % - 100 % and summarized by treatment group.

2.4.2 Prior, concomitant and post therapies

The following summaries for COPD-related medications will be performed separately for medications prior to run-in (medications starting prior to screening and ending prior to or at the run-in visit) and for concomitant medications (medications which were taken anytime between the first dose and last dose of randomized treatment, inclusive). COPD-related medications will be summarized by pre-specified drug categories, route of administration, preferred term, and treatment group.

Non-COPD related medication prior to and after the start of randomized treatment will be summarized by route of administration, preferred term, and treatment group.

Surgical and medical procedures (non-drug therapies) are coded using MedDRA. Presentations will be done by MedDRA primary system organ class and preferred term, separately for prior and concomitant procedures.

2.5 Analysis of the primary objective

The primary objective of this study is to characterize the DR (dose-response) efficacy relationship among QBW251 doses (25, 75, 150, and 300 mg b.i.d.) and placebo with regards to the change from baseline in trough FEV₁ after 12 weeks of treatment. The goals associated with this objective are below.

- To confirm an overall DR signal

- To estimate the dose(s) that corresponds to the target effect over placebo based on the estimated DR curve

Due to early termination of the 450 mg, analysis of the primary endpoint will not include the 450 mg dose.

2.5.1 Primary endpoint

The primary estimand, defined below, quantifies a hypothetical on-treatment Week 12 effect during stable periods (i.e. outside episodes of COPD worsening that require rescue medication or systemic corticosteroids). This estimand targets the maximum treatment effect for QBW251 and allows selection of the best dose for those who take it for 12 weeks.

- **Population:** patients with moderate to severe COPD enriched for presence of chronic bronchitis and a history of exacerbations and treated with LABA/LAMA/ICS background therapy
- **Variable:** trough FEV₁ (average of the 2 values taken 15 and 45 min pre-dose) change from baseline after 12 weeks of treatment
- **Intervention effect of interest:** Effect of interventions initiated at randomization during stable periods (i.e. outside episodes of COPD worsening that require rescue medication or systemic corticosteroids) and that would have been observed had all patients remained on their assigned treatment for 12 weeks, with the following post-randomization events accounted for by assessing:
 - Intake of rescue medication or systemic corticosteroids (SCS): the effect outside of periods of worsening disease that necessitate rescue medication or SCS
 - Discontinuation of study treatment or study participation: hypothetical on-treatment trough FEV₁ value.
 - Missing data due to any reason prior to completion or discontinuation of treatment: on-treatment trough FEV₁ values.
- **Summary measure:** mean difference between treatment groups (QBW251 compared with placebo)

The baseline value is defined as the average of the FEV₁ values taken approximately 45 and 15 minutes prior to first dose of randomized treatment at Day 1. If one of the 2 values is missing (or is not confirmed to be pre-dose) then the remaining non-missing value will be taken as the baseline. If both values are missing (or are not confirmed to be pre-dose), then the measurements taken at the Run-In 1 visit will be used as the baseline.

2.5.2 Statistical hypothesis, model, and method of analysis

The Multiple Comparison Procedure – Modelling (MCP-Mod) methodology (see [Bretz et al 2005](#) and [Pinheiro et al 2014](#)) will be employed to assess the primary objective. An overview of the steps for the MCP-Mod methodology is given below.

Step 1 (Testing an overall dose-response signal - MCP part):

The (covariate) adjusted mean responses at each individual dose will be obtained from a mixed-effect linear model for repeated measures (MMRM) with terms for baseline FEV₁, visit, region,

treatment, smoking status at screening, severity of airflow limitation, run-in post-bronchodilator FEV₁, treatment-by-visit interaction, and baseline FEV₁-by-visit interaction as fixed effects. To allow adjustment for correlations between time points within patients, an unstructured variance-covariance structure will be used. The estimated treatment difference and the associated 90% confidence intervals will be presented for the treatment contrast of each dose versus Placebo.

[figure not shown]
The adjusted treatment means from the MMRM will be used to test the null hypothesis of a flat DR relationship for the primary efficacy endpoint at a one-sided significance level of 5% against the alternative hypothesis of a non-constant DR curve. The testing will be performed with a multiple contrast test described in the MCP-Mod methodology.

A wide range of possible dose-response relationship will be considered to take model uncertainty into account (Figure 2-1). A monotonic DR is assumed, supported by preclinical data and the observed DR of another CFTR-potentiator, ivacaftor. Eleven candidate DR curves (4 Emax, 4 Sigmoid Emax, 2 Exponential, and 1 Linear) will be used to derive the optimal model contrasts for the multiple contrast tests. Emax and sigmoidal Emax models are considered based on the observed DR of ivacaftor (FDA 2012). The ED50 values (the dose at which half of the maximum effect is reached) for the Emax models will be 25, 75, 150, and 300. The parameters of the sigmoidal Emax models (ED50, h) will be (25, 3), (75, 3), (150, 3) and (300, 3) where h is the Hill parameter that determines the steepness of the dose-response shape. Exponential models are considered since there is an over-proportional increase of exposures at the high end of the dose range tested. The parameter controlling the convexity of the Exponential models will be 150 and 300.

For each of the 11 candidate DR curves, a contrast test statistic will be derived that maximizes the power assuming the true mean response is the one assumed by the candidate DR curve. The detection of a significant DR signal is based on the maximum of the 11 contrast test statistics. The overall null hypothesis of no DR relationship is rejected if the multiplicity adjusted p-value for at least one contrast test is < 0.05 (one sided).

For each candidate DR curve, the test statistics and corresponding adjusted p-values will be presented.

Figure 2-1 Candidate Dose Response Curves

Due to termination of the 450 mg b.i.d. arm candidate curves Emax(ED50=300), SigEmax(ED50=300) and Exponential(delta=300) may no longer be appropriate for MCP-Mod analyses that do not include the 450 mg b.i.d. arm. These candidate curves will be removed and the Exponential(delta=75) will be added.

Step 2 (Estimation of the dose-response curve and target dose – Mod part):

Once the DR signal is declared, the DR curve and the target dose(s) of interest will be estimated by model averaging. A large number of bootstrap samples from the multivariate normal distribution will be drawn with adjusted means from the MMRM and corresponding covariance matrix. For each sample:

- DR models from the candidate families (Emax, Sigmoid Emax, Exponential, Linear) will be fitted to the data and the best model according to the generalized Akaike information criterion (AIC) will be chosen.
- The predictions for dose-response will be obtained from the best model for each sample.

The final DR curve estimate is the median of these predictions while confidence intervals will be calculated from the quantiles. The final DR curve estimate with the model-based two-sided 90% confidence interval will be presented graphically. In addition, the plot will include the mean responses from the MMRM and the associated 90% confidence intervals for each of the studied dose groups.

The target dose(s) that corresponds to a clinically relevant effect over placebo can be estimated using inverse regression techniques ([Bretz et al 2005](#)). The target dose will be estimated for a delta of 50ml and presented graphically within the estimated DR curve.

All data related to safety, efficacy and other assessments including PK exposure will be taken into consideration to propose a dose for Phase 3.

2.5.3 Handling of missing values/censoring/discontinuations

Since the estimand is related to an effect outside of rescue med intake, spirometry measurements within 6 hours of rescue medication or within 7 days of intake of SCS use will be set to missing. If one of the values contributing to the trough FEV₁ variable is missing at a visit, the remaining non-missing value will be taken as trough FEV₁. If both values are missing, then their trough FEV₁ will be regarded as missing at that visit.

For the primary analysis, only on-treatment data (from date of first randomized dose up to 1 day after date of last randomized dose) will be used as the estimand specifies a hypothetical on-treatment effect. Missing on-treatment data will not be explicitly imputed as the MMRM model implicitly imputes missing data assuming the missing at random (MAR) mechanism.

The imputation procedure(s) related to the trough FEV₁ supportive analyses ([Section 2.5.4](#)) are "jump-to-reference" (J2R) and MAR ([Carpenter et al 2013](#)). The imputations will be based on all available data (i.e. from all scheduled time points) using all covariates as specified in the MMRM. For J2R, only placebo (reference) data will be used. For MAR, data from the same treatment arm will be used for building the imputation model. Imputation of intermittent missing observations before treatment discontinuation will be carried out following a MAR mechanism for all treatment arms. Additional details are provided in [Section 5.7](#).

2.5.4 Supportive analyses

A supplementary analysis will be performed that quantifies the treatment effect in all randomized patients during stable periods (i.e. outside episodes of COPD worsening that require rescue medication or SCS) with an adherence to treatment like we would see in clinical practice in a world without COVID-19, with the following post-randomization events accounted for by assessing:

- a. Intake of rescue medication or systemic corticosteroid: effect outside of periods of worsening disease that necessitate rescue med or systemic corticosteroid
- b. Discontinuation of study treatment for non-COVID-19 related reason with follow-up: actual off-treatment value. If no data was retrieved after study treatment discontinuation, missing data will be multiply imputed based on placebo arm data: J2R assumption for the QBW251 arms and MAR assumption for placebo arm.
- c. Discontinuation of study treatment due to a COVID-19 related reason: on-treatment value. Missing data will be multiply imputed based on the MAR assumption.
- d. Discontinuation of study participation due to any non-COVID -19 related reason: off-treatment value. Missing data will be multiply imputed based on placebo arm data: J2R assumption for the QBW251 arms and MAR assumption for placebo arm.

- e. Any other event leading to missing data prior to completion or discontinuation of study treatment: on-treatment value. Missing data will be multiply imputed based on the MAR assumption.

Results will be presented similarly to those of primary analyses.

Details are provided in [Section 5.7](#).

A supportive analysis will be performed including the 450mg dose and only data up to week 12. This will be done similarly as the primary analysis, however in addition candidate curves Emax(ED50=300), SigEmax(ED50=300) and Exponential(delta=300) will be considered.

A supportive exposure-response analysis may be performed outside the CSR.

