1.1 Study design

[figure not shown]
This study uses a 6 treatment arm, parallel-group, randomized, double-blind study design. One treatment arm (450 mg b.i.d.) was discontinued after reaching a pre-defined stopping criterion (see Section 12.7.1 of the protocol) at the first DMC interim analysis.

Patients initially undergo a screening period of 1 week. This screening period (Weeks -3 to -2) serves to assess eligibility and to taper patients off disallowed medications. Subsequently, patients enter the run-in period (2 weeks; Days -14 to 1) to establish baseline values for symptom assessments, to standardize the COPD background therapy (triple combination LABA/LAMA/ICS), and to complete eligibility assessments. At visit Run-In 2 final eligibility will be assessed. Eligible patients will move into the Day 1 visit where they will be randomized. Day 1 also generates additional baseline data and study treatment is initiated. The treatment period consists of 24 weeks, during which the patient returns to the site for regular visits (Day 1 – Week 24). Upon completion of the treatment period, patients are followed up for safety assessments during the Follow-Up period (Weeks 25 – 28).

Approximately 956 male and female COPD patients are randomized into 1 of 6 treatment arms with a randomization ratio of 2:2:1:1:1:2 (450 mg b.i.d. (discontinued), 300 mg b.i.d., 150 mg b.i.d., 75 mg b.i.d., 25 mg b.i.d., placebo). Detailed information regarding sample size calculation is provided in [Section 3](#). After reaching the pre-defined exposure-based stopping criterion, patients were no longer randomized to the 450 mg b.i.d. treatment, resulting effectively in a 2:1:1:1:2 randomization ratio (300 mg b.i.d.:150 mg b.i.d.: 75 mg b.i.d.: 25 mg b.i.d.: placebo) from the day of 450 mg b.i.d. discontinuation (20-Apr-2020) onward.

Randomization will be stratified by smoking status (current or ex-smoker) and severity of airflow limitation (FEV₁ \geq 30% to $<$ 50% and \geq 50% to $<$ 80%).

Figure 1-1 Study design

The primary endpoint will be assessed after 12 weeks of treatment.

Interim analyses (IA) on safety data are planned for an independent external safety data monitoring committee (DMC) to evaluate the results of pre-specified interim PK and safety data. Up to 5 DMC IAs are proposed to occur. Detailed information regarding DMC analysis will be provided in the DMC charter and a separate DMC SAP.

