2.1.1.4 Handling early termination of the 450mg b.i.d arm

If not stated otherwise, all efficacy inferential analyses will not include the 450 mg dose due to early termination of the 450 mg b.i.d arm, resulting in very few or no data in some of the strata (covariates/factors in the model) during the later visits. All descriptive summaries will include the 450 mg b.i.d. dose.

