significance level across all analyses is maintained at 0.05. At each interim analysis, an exact test on the proportion of subjects who exceed the exposure threshold will be performed to test the following hypotheses for these 2 treatment arms.

- Null hypothesis (Ho): the proportion of patients exceeding the exposure threshold $< 5\%$
- Alternative hypothesis (Ha): the proportion of patients exceeding the exposure threshold $\geq 5\%$

The interim analyses are proposed to occur when approximately 20%, 40%, 60%, 80%, and 100% of subjects have completed at least 4 weeks of treatment, which should be long enough to determine if the patient's exposure will exceed the threshold or not. The corresponding stopping boundaries in the p-value scale are 0.015, 0.016, 0.017, 0.018, and 0.019 for the interim analyses. For example, when the first interim analysis is performed after 20% patients have completed 4 weeks of treatment in the 450 mg b.i.d. arm, the observed (i.e. nominal) p-value has to be equal to or smaller than 0.015 in order to reject Ho and terminate the treatment arm.

If the true proportion of patients in the 300mg or 450 mg b.i.d. treatment arm exceeding the exposure threshold is $< 5\%$, then the probability of rejecting Ho would be very low ($< 5\%$) with this group sequential test for the treatment arm. If the true proportion is 10% then the probability of rejecting Ho and stopping the treatment arm early would be high ($> 77\%$). If the timing of the actual interim analyses deviate from the proposed schedule (20%, 40%, 60%, 80%, and 100% completing at least 4 weeks of treatment), stopping boundaries will need to be recalculated using the pre-specified α -spending function and based on the actual sample size at each interim analysis. The observed p-values at the interim analyses will then be compared against the recalculated stopping boundaries.

More details will be outlined in the DMC charter and a separate DMC SAP.

After reviewing the exposure data from the first interim analysis, the DMC informed the sponsor that the 450 mg b.i.d. arm had crossed the stopping boundary and recommended termination of the treatment arm. The DMC confirmed that the arm was well tolerated in this patient population and the stop was not based on adverse reactions to the 450 mg b.i.d. regimen. The sponsor followed the DMC's recommendation and discontinued investigational treatment from all patients randomized to the 450 mg b.i.d. arm.

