2.13.2 Efficacy

Up to 2 IAs on efficacy data may be conducted and the timing will correspond to 1 or 2 safety DMC analyses. The purpose of these IA(s) is to have an early assessment of the data for planning future studies in the QBW251B program. The efficacy IA results will not trigger any change or decision in the conduct of this study.

An internal Novartis committee, external to the study team, will be set up to review the both the efficacy and safety data. Once team members are exposed to the unblinded IA data, they will no longer be involved in the further execution of the study. A charter will provide further details.

The first IA will be conducted when approximately 645 to 680 patients, including the ~102 patients randomized to the 450mg b.i.d. arm, have either discontinued or completed 12 weeks of treatment. This IA will have acceptable precision for the estimated trough FEV₁ dose-

response curve. The average half-length of the 90% confidence interval is around 26 mL and 32 mL for the estimated dose-response curve and the estimated placebo-adjusted dose-response curve, respectively. If the first IA does not lead to a clear decision for the planning of the QBW251B program, a second IA may be performed when all randomized patients have either discontinued or completed 12 weeks of treatment.

For efficacy, the interim analyses will include all data up to the cut-off date for the IA.

An analysis may be planned and reported separately on the relationship between measured plasma trough concentrations and trough FEV1 change from baseline as described in Section 2.10.

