randomized to the 450 mg b.i.d. arm prior to its discontinuation. Prior to the discontinuation of 450mg b.i.d., patients were randomized to QBW251 450, 300, 150, 75, 25 mg b.i.d., or placebo with an allocation ratio of 2:2:1:1:1:2. After discontinuation of 450mg b.i.d., patients were randomized to QBW251 300, 150, 75, 25 mg b.i.d., or placebo with an allocation ratio of 2:1:1:1:2. This sample size of 854 (956 total minus approximately 102 patients already randomized to 450 mg b.i.d.) achieves at least 80% power for dose-response signal detection on key endpoints for all models from the candidate set based on the MCP-Mod methodology and also to ensure an acceptable precision for the DR curve estimation. The calculations in [Table 3-1](#) exclude 450 mg b.i.d. from the analysis and are based on a 20% dropout rate, a one-sided significance level of 5%, and the following standard deviation assumptions.

- Pre-dose trough FEV₁: A common standard deviation of 200 mL based on previous Novartis COPD studies.
- E-RS Cough & Sputum weekly mean score: A common standard deviation of 1.3 based on the FLAME study ([Wedzicha et al 2016](#)).

Table 3-1 Power and Precision

Variable	Maximum improvement over placebo	Power to detect a DR signal	Average half-length of 90% confidence interval	
			Estimated DR curve	Estimated placebo-adjusted DR curve
Trough FEV ₁	60 mL	92%	21 mL	26 mL
	50 mL	81%		
E-RS Cough & Sputum	0.35	86%	0.14	0.17
	0.30	76%		

Power calculations were performed using ADDPLAN-DF-4.0 and the precision estimates (half-length of confidence interval) were obtained from simulations.

The randomization ratio was generally based on D-optimality criteria, which maximize the information on the dose-response curve, for the MCP-Mod analysis. The D-optimal allocation ratio randomizes approximately twice as many patients to placebo and the highest dose, compared to the middle doses.

4 Change to protocol specified analyses

Analysis of the primary endpoint:

Due to termination of the 450 mg b.i.d. arm, candidate curves E_{max}(ED₅₀=300), SigE_{max}(ED₅₀=300) and Exponential(delta=300) may no longer be appropriate for MCP-Mod analyses that do not include the 450 mg b.i.d. arm. These candidate curves will be removed and the Exponential(delta=75) will be added.

5 Appendix

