5.7 Statistical models

5.7.1 Primary analysis

The following MMRM ANCOVA will be used for trough FEV₁:

Dependent variable = intercept + treatment + region + baseline FEV₁ + smoking status at screening + severity of airflow limitation + run-in post-bronchodilator FEV₁ + visit + treatment*visit + baseline value*visit + error.

The within-patient correlation will be modeled using an unstructured covariance matrix in the mixed model. The Kenward-Roger approximation will be used to estimate denominator degrees of freedom ([Kenward and Roger, 1997](#)).

If the model fails to converge with unstructured covariance matrix, either a compound symmetry (first choice) or first order autoregressive (AR1) (second choice) covariance structure will be used. For the efficacy IA, if the model still fails to converge only data up to week 12 will be included.

The SAS procedure PROC MIXED will be used for analysis. Results will be presented with LSM and standard error (SE) for treatment effects and LSM, SE, associated two-sided 90%

confidence interval, and two-sided p-value for treatment contrasts of each QBW251 dose versus Placebo.

• **MCP-Mod**

The Multiple Comparison Procedure – Modelling (MCP-Mod) methodology (see [Bretz et al 2005](#) and [Pinheiro et al 2014](#)) will be employed to assess the primary objective. The following steps for the MCP-Mod methodology will be performed. The analysis will be implemented in SAS (used for MMRM) and R (MCP-Mod) using DoseFinding R package:

Step 1 (Testing an overall dose-response signal - MCP part):

- a. Fit MMRM model. Extract estimates and variance-covariance matrix at Week 12 from fitted model.
- b. Perform multiple contrast test with pre-defined model types and optimal contrasts, using variance-covariance matrix at Week 12 from the MMRM.

Consider the following candidate models:

- Emax (ED50=25)
- Emax (ED50=75)
- Emax (ED50=150)
- sigEmax (ED50=25, h=3)
- sigEmax (ED50=75, h=3)
- sigEmax (ED50=150, h=3)
- exponential (delta=75)
- exponential (delta=150)
- linear

Present T-statistics and corresponding adjusted p-values for each candidate model.

If there is at least one significant DR relationship, the DR signal is declared and Step 2 will be performed.

Step 2 (Estimation of the dose-response curve and target dose – Mod part):

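### The supportive MCP-Mod analysis that brings 450 mg back has no randomisation-period term, although by planned counts about 58% of the other arms were randomised after 450 mg closed

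*SAP*

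**What the plan says.** - **The analysis.** SAP 2.5.4: "A supportive analysis will be performed including the 450mg dose and only data up to week 12". It is otherwise done like the primary analysis, with three candidate curves added (Emax 300, sigmoid Emax 300, exponential 300).
- **The model.** SAP 5.7.1 begins "Dependent variable = intercept + treatment + region + baseline" FEV1 and continues with smoking status, airflow-limitation severity, run-in post-bronchodilator FEV1, visit, treatment-by-visit and baseline-by-visit. Neither there nor in SAP 2.5.2 is there a term for randomisation period or calendar time.
- **Closure of 450 mg.** SAP 1.1: "patients were no longer randomized to the 450 mg b.i.d. treatment, resulting effectively in a 2:1:1:1:2 randomization ratio", from 20-Apr-2020 onward, that day included. SAP 2.13 (safety interim analyses) adds that the sponsor "discontinued investigational treatment from all patients randomized to the 450 mg b.i.d. arm".
- **Counts.** SAP 3 gives 854 patients outside 450 mg ("956 total minus approximately 102 patients already randomized to 450 mg b.i.d"), with allocation 2:2:1:1:1:2 before closure and 2:1:1:1:2 after.
- **Data used.** SAP 2.5.3 limits the primary model as follows: "only on-treatment data (from date of first randomized dose up to 1 day after date of last randomized dose) will be used".
- **Default handling of 450 mg.** SAP 2.1.1.4 leaves 450 mg out of efficacy inference unless stated otherwise, because its early termination is described as "resulting in very few or no data in some of the strata" at later visits. SAP 2.5.4 is such an exception.
- **Time-related analyses.** SAP 2.14 summarises baseline data by time of enrolment and repeats the FEV1 MMRM by region and by enrolment before or during the pandemic. Those periods follow regional or country dates.

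**The concern.** Every 450 mg patient was randomised before 20-Apr-2020, while more than half of the placebo and 300 mg patients were to be randomised on or after that date. SAP 2.5.4 does not restrict the comparison to patients who could have been allocated to 450 mg. In this model, dose is therefore partly confounded with enrolment period, and only at 450 mg. If the later cohort's 12-week FEV1 change differs for reasons other than drug, and the covariates do not absorb the difference, the model reads part of it as an effect of 450 mg. That shifts the top point of the fitted curve and moves the contrast test off its nominal level.

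The protocol (4.2) included 450 mg because nothing indicated that 300 mg had reached the plateau. The supportive analysis is where a reader would look for that answer, and SAP 2.5.2 says all efficacy data will feed the Phase 3 dose proposal.

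**Working it through.** **Plan's own figure.** Simulating the multiple contrast test without 450 mg (854 patients, 20% dropout, split 2:1:1:1:2, SD 200 mL for FEV1 and 1.3 for E-RS, one-sided 5%, 11 curves, minimum power over the set) gives 92.4% and 81.6% for FEV1 at 60 and 50 mL. For E-RS it gives 86.4% and 75.9%. SAP Table 3-1 has 92%, 81%, 86% and 76%, so the inputs are read correctly.

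**Non-concurrent share.** 102 patients at 2 of 9 allocation units is 51 per unit.
- Other arms before closure: 7 × 51 = 357.
- On or after closure: 854 − 357 = 497, and 497/854 = 58.2%.
- Placebo alone, and likewise 300 mg: 102 before and 142 after, of 244; the share is the same.
- The 450 mg count is approximate: 97 to 107 patients gives 60.5% to 55.9%.
- The SAP does not say whether this analysis is also run at the first efficacy interim (645 to 680 patients, "including the ~102 patients randomized to the 450mg b.i.d. arm"). If it is, 102 × 9/2 = 459 were randomised by closure. The share is then (645 − 459)/(645 − 102) = 34.3% to (680 − 459)/(680 − 102) = 38.2%.

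**Bias.** Let d be the early-minus-late shift left after the covariates. All 450 mg patients are early, against 41.8% of placebo and of 300 mg, so the bias is d × (1 − 0.418) = 0.582d. The documents give no d. Assumed values of 10, 20 and 30 mL give 5.8, 11.6 and 17.5 mL. The target effect in SAP 2.5.2 is 50 mL.

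**Standard error of 450 mg minus placebo.** Placebo evaluable = 244 × 0.8 = 195.2. The evaluable 450 mg count is not given. I take 20, 41, and 102 × 0.8 = 81.6 (about 82); the last applies the plan's dropout and ignores that dosing was stopped in the whole arm.
- Without a period term: 200 × √(1/n + 1/195.2).
- A period term adds 0.582² × 200² × (1/285.6 + 1/397.6) = 81.5 to the variance, where 285.6 = 357 × 0.8 and 397.6 = 497 × 0.8.

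| Evaluable 450 mg | SE without term | SE with term | Increase |
|---|---|---|---|
| 20 | 47.0 mL | 47.8 mL | 2% |
| 41 | 34.4 mL | 35.5 mL | 3% |
| 82 | 26.4 mL | 27.9 mL | 6% |

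These are simple Week 12 counts; the MMRM would recover some information from Weeks 4 and 8.

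**False-positive rate, flat truth, one-sided 5%.** Twelve optimal contrasts (the nine in SAP 5.7.1 plus the three added), critical value about 2.1, multivariate normal simulation:

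| d | 20 evaluable | 41 | 82 |
|---|---|---|---|
| 10 mL | 5.7% | 6.2% | 6.9% |
| 20 mL | 6.6% | 7.8% | 9.6% |
| 30 mL | 7.6% | 9.8% | about 13% |
| −20 mL | 3.9% | 3.3% | 2.7% |

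With the period term the rate returns to 5% in every cell.

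**If drift follows assessment date instead.** Suppose a 20 mL step applies to all 450 mg Week 12 values and to a fraction q of early controls, with q = 20/81.6 = 0.245 or 41/81.6 = 0.50. Bias is 20 × (1 − 0.418q) without the term and 20 × (1 − q) with it.
- 20 evaluable: 18.0 falls to 15.1 mL; false positives 7.8% to 7.1%.
- 41 evaluable: 15.8 falls to 10.0 mL; false positives 9.2% to 7.1%.

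The dates show why. If 450 mg dosing ended on 20-Apr-2020 (an assumption), on-treatment values stop on 21-Apr-2020. Day 72, where the Week 12 window opens in SAP 5.2, is then reached only with a first dose by 10-Feb-2020 (71 days earlier). A control randomised on 19-Apr-2020, the last concurrent day, reaches Day 85 on 12-Jul-2020 (84 days later).

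**The case against.** The case for leaving the plan alone has four parts.

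- **Little rests on it.** This is one supportive analysis with no decision rule. The default in SAP 2.1.1.4 already concedes that 450 mg data are thin. This stands and limits the point to an optional improvement.
- **The harm is assumed.** Neither the drift nor the evaluable count is in the documents, and the bias is well below one standard error at every assumed shift (5.8/47.0 = 0.12 up to 17.5/34.4 = 0.51 for 20 and 41 evaluable, and 17.5/26.4 = 0.66 for 82). This also stands. A reader might infer that the test is inflated; the documents show only that it is exposed, and a shift the other way makes it conservative.
- **Time is partly handled.** The endpoint is change from each patient's own baseline, the model adjusts for several covariates, and SAP 2.14 repeats the MMRM by time of enrolment. These can reduce or reveal drift, but they do not adjust the 450 mg contrast. The SAP 2.14 periods follow regional pandemic dates, not the closure date, and 450 mg is excluded there by default. Following the primary analysis need not mean copying it exactly, but no period term is specified.
- **The remedy is incomplete.** The one time influence the SAP names is COVID-19, which could act by assessment date. With 20 evaluable patients the term then removes only 18.0 − 15.1 = 2.9 mL of 18.0 mL. This stands and must be reported as a limitation.

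**Conclusion.** The concern holds within narrow limits. By planned counts, assuming exact allocation, about 58% of the non-450 mg patients in this supportive analysis are non-concurrent, and the specified model does not account for it. An assumed residual shift of 20 mL gives 11.6 mL of bias at 450 mg and, when it favours the early cohort, a false-positive rate of about 6.6% to 9.6% over 20 to 82 evaluable patients. At the first efficacy interim the same shift would give 20 × 0.343 = 6.9 to 20 × 0.382 = 7.6 mL.

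A reader might infer that closing an arm mid-trial also compromises the primary dose-response analysis. The documents do not support that: the primary analysis excludes 450 mg, and allocation among its five arms was 2:1:1:1:2 in both periods. Nor do they support reading this as the main weakness of the supportive analysis, since sparse on-treatment 450 mg data at Week 12 matters more. The change is worth considering because it is cheap, not because an error has been shown.

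**What to change.** In the SAP 2.5.4 analysis with 450 mg only:

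1. Add randomisation period (before versus on or after 20-Apr-2020, matching SAP 1.1) and period-by-visit to the MMRM. Take the dose means and Week 12 covariance for MCP-Mod from that model.
2. Report a check restricted to patients randomised before 20-Apr-2020. Its standard error for 450 mg versus placebo is 200 × √(1/n + 1/81.6): 49.9, 38.3 or 31.3 mL for 20, 41 or 82 evaluable.
3. Report the number of 450 mg patients with on-treatment Week 12 data.
4. State that drift by assessment date is only partly removed, in the restricted check as well.
5. Say whether this analysis is also run at the efficacy interims.

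The cost is a few SAP sentences and two model terms. The standard error of 450 mg versus placebo rises by about 2%, 3% or 6% at 20, 41 or 82 evaluable patients. The primary analysis needs no change.
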